Primary/Secondary Objective(s):	
Primary objective: To determine and compare the median complete protection time (CPT) of two insect repellent products and a positive control against Culicoides nubeculosus (midges).
 
Secondary objective: To determine and compare the protective efficacy of two insect repellent products and a positive control against Culicoides nubeculosus (midges).
		
Study Design / Methodology:	A single-centre laboratory setting study using healthy volunteers to test two insect repellent products (NEO-PART prolonged action release technology PMD (40% PMD) And NEO-PART prolonged action release technology PMD (35% PMD)) and a Positive control product (20% Picaridin, 'Smidge') against Culicoides nubeculosus midges.		
Number of Participants:	A total of 7 volunteers will be used to determine the median Complete Protection Time and protective efficacy of two insect repellents and a positive control against one midge species.		
Intended Product Users:	The test products are designed for use by the general public in areas where midge biting is likely.		
Study Duration:	
Participants will undergo a screening evaluation which includes a bite test (monitored for up to 72 hours), followed by up to 3 repellency tests of up to 12 hours duration. Each participant will be followed up after each visit by email/ in person/ by phone within 72 hours of the visit to monitor for adverse events. The minimum interval between the two repellency tests will be 72 hours. The minimum duration of participant involvement would therefore be approximately 3 weeks.
 
Total study duration (recruitment and participant involvement) is anticipated to be 1 month.
		

Inclusion Criteria:
	
 • Able and willing to give fully informed consent; • Able to understand and comply with the study procedures; • Consider themselves to be in good general health; • Male or female; • Aged 18 to 65 years; • Non-smokers or willing to refrain for 12 hours prior to and during each test; • Willing to undergo a bite test with Culicoides nubeculosus midges with up to 72 hour follow-up.

Exclusion Criteria:
	
 • Suspected or known to be sensitive or allergic to midge bites; • Participated in an interventional study (other than a biting insect challenge study) in the previous 3 months; • Participated in a biting insect challenge study in the previous 72 hours; • Aware of having any cardiovascular or respiratory disorder (whether active or inactive) (e.g. asthma); • Individuals with localized skin disorders affecting the forearm; • Allergic to any of the test product ingredients; • Extensive tattooing or other conditions of the forearm which would make interpretation of the bite test results difficult; • Women who are pregnant, nursing or intending to become pregnant; • Previous anaphylaxis; • Aware of having a compromised immune system;(an immune system that is temporarily or permanently incapable of working at full capacity); • Phobia of flying insects; • Travelled to a mosquito-borne disease endemic area in the last 3 months.

Efficacy Endpoint(s):
	
Primary: Median Complete Protection Time for the repellent products, tested against Culicoides nubeculosus midges.
 
Secondary: Percentage protective efficacy of the repellent products, tested against Culicoides nubeculosus midges.

Safety Endpoint(s):
	
Adverse event data will be collected and summarised.

Statistical Methods:
	
Median Complete Protection Time will be calculated using the Kaplan Meier survival-function.
 
Two-way analysis of variance followed by Tukey's tests or general linear mode will be used to compare the mean complete-protection time for the tested repellents

Investigation Site(s):
	
Single-centre: Arthropod Control Product Test Centre (arctec), Chariot Innovations Limited, a wholly-owned subsidiary of the London School of Hygiene & Tropical Medicine (LSHTM).

TABLE OF CONTENTS

1. INTRODUCTION.....	7
2. OBJECTIVES.....	7
3. STUDY DESIGN	7
3.1. STUDY ENDPOINTS.....	8
3.2. RISKS AND BENEFITS	8
3.2.1. Midges	8
3.2.2. Product	8
4. PARTICIPANT ENTRY	9
4.1. SCREENING PROCEDURES	9
4.2. INCLUSION CRITERIA	9
4.3. EXCLUSION CRITERIA	10
4.4. WITHDRAWAL CRITERIA.....	10
5. RANDOMISATION AND ENROLMENT	11
6. TREATMENTS	11
7. SAFETY REPORTING FOR NON-DRUG TRIALS.....	12
7.1. DEFINITIONS	12
7.2. REPORTING PROCEDURES	12
7.2.1. Non serious AEs	12
7.2.2. Serious AEs	12
8. TEST METHODOLOGY.....	13

APPENDIX 3: FLOWCHART FOR SAFETY REPORTING24

APPENDIX 4: SAMPLE SIZE CALCULATION FOR A COMPARISON TRIAL BETWEEN A POSITIVE CONTROL AND TWO MIDGE REPELLENT PRODUCTS.....25

1. Introduction

Mosquitoes, midges and other biting insects are vectors of extremely important diseases such as malaria, yellow fever, filariasis and many viruses and also may be of great nuisance value. The use of repellent products can provide added personal protection from disease transmission and nuisance bites. New effective repellents would offer an additional option for protection against biting insects. The tests carried out by *arctec* provide important information on the effectiveness of skin repellents, which will be used for label claims to accurately inform consumers and registration purposes.

The aim of this study is to determine the effectiveness of two topically applied insect repellent products provided by NEO-INNOVA HEALTHCARE LIMITED and one positive control containing the UK repellent brand 'Smidge'.

2. Objectives

Primary objective: To determine and compare the median complete protection time (CPT) of two insect repellent products and a positive control against *Culicoides nubeculosus* (midges).

Secondary objective: To determine and compare the protective efficacy of two insect repellent products and a positive control against *Culicoides nubeculosus* (midges).

3. Study Design

This is a single-centre, single-arm study with all participants testing two formulations containing PMD and a positive control product containing Picaridin. The control for each test is an untreated arm. There is no blinding or randomisation employed, since the outcome measures are based on midge behaviour. Repellent product testing takes place in a laboratory setting using 7 participants (preferably gender balanced). Each participant will test both PMD formulations and a positive control product (see section 8).

- *Culicoides nubeculosus* is a common species of biting midges belonging to the family Ceratopogonidae. *Culicoides* midges are small biting flies found throughout the world, breeding primarily in moist, damp, muddy habitats. To develop their eggs, female *Culicoides* require a blood meal from warm-blooded vertebrates, most often a domesticated animal and humans. *Culicoides* are implicated in the transmission of multiple zoonotic diseases, such as bluetongue virus, African horse sickness, and bovine ephemeral fever, and their bites can be painful and can cause uncomfortable irritation to both humans and livestock.

Midges will be obtained from insecticide-susceptible reference strains held at the Pirbright Institute (Institute for Animal Health). They will be maintained at 22-24°C, 80-90% relative humidity, with a 12:12 hour photoperiod.

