3.2. Risks and Benefits

3.2.1. Midges

Participants will be exposed to insect bites and may experience some irritation and itching. The midges are reared in insectaries and have been in culture for many years and are pathogen free. In order to minimise the risk of infection the following steps have been taken:

- Midges used in the test are 3-8 days old and have never had a blood meal.
- One cage of midges is used on one volunteer only and after the test, those midges are destroyed. Therefore, no two volunteers are ever bitten by the same midges and the midges are never returned to the colony.
- There will be a minimum of 72 hours between product tests in order to minimise any possibility for sensitization to midges bites

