4.4. Withdrawal Criteria

Participants can stop at any time without giving a reason for withdrawing. Data collected to the point of withdrawal will be used in the analysis of the study, unless the participant requests that their data is not used, in which case it will be removed from the database. Participants may also be removed at the discretion of the Chief Investigator, where continued participation may affect the safety of the participant or where there is a development of any condition which might interfere with study participation.

5. Randomisation and Enrolment

Volunteers will be recruited through standard recruitment methods, including emails, posters, leaflets and other advertising routes to staff and students of LSHTM and other members of the public. Volunteers will be fully informed before the study and it will be made clear that they can withdraw from the study at any time. Volunteers will be given and asked to read the Participant Information Sheet and Product Information Sheet which describes the tests which they will take part in, and a consent form which must be signed before the test begins.

6. Treatments

NEO-INNOVA HEALTHCARE LIMITED will provide two products to be tested containing 35% and 40% PMD, and one positive control containing 20% Picaridin. The positive control product is currently marketed as a midge repellent, while PMD is a recommended active ingredient, which has been evaluated for safe use by the U.S. Environmental Protection Agency (USEPA)¹. Therefore, humans have already used the products. The products will be applied at a rate of 1.67 $\mu\text{l}/\text{cm}^2$. The products will be applied to the measured forearm of each participant. This dose does not exceed the maximum daily limit for PMD or Picaridin.

7. Safety Reporting for Non-Drug Trials

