7.2.2. Serious AEs

Regardless of the relation of the adverse event to study participation, the event must be reported as a serious adverse event if it meets any of the definitions in section 7.1. AE questionnaires meeting the SAE definition will be

submitted to [name] within 24 hours. SAEs that are assessed by the CI as being both related and unexpected must be reported to the LSHTM EC within 15 days of the CI becoming aware of the event.

In the case of a severe reaction such as anaphylaxis, it will be treated as an emergency and an ambulance will be called immediately by dialling 999 directly from a mobile, or 555 from an internal phone (this is the emergency line at reception who will then dial 999). In addition, a trained First Aider within the [name] building will be called. Designated First Aider is [name] ([name]), but if they are unavailable First Aiders are contactable through internal phones by typing in 'first aid' to the internal phone book which will bring up a list of registered First Aiders. All *arctec* staff ([name] [name], [name] [name], [name] [name]) and some of the other insectary staff ([name] [name]) have also been trained in anaphylaxis.

In the event of an acute allergic reaction, a trained First Aider within the [name] building will be called and the member of staff present will remove the trigger if possible. This will include removing any biting mosquitoes and washing the product off the participant's arm.

8. Test methodology

Female midges will be host-seeking, of uniform age and 3-8 days post-emergence. Active host-seeking females will be selected to ensure a good response from the test midges using an aspirator or an appropriate airflow apparatus.

Fifty female midges will be placed into a cage 20x20x20cm inside the testing room at least one hour before the test commences. Testing should be conducted in a testing room maintained at 25±2°C and 80% RH.

The researcher will verify that the participant has adhered to the pre-testing instructions. Non-compliant participants will be unable to participate in the test on that day and will be booked in for another appointment.

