8.1. Midge Fitness Check and control test (combined)

Before the start of each test, the participant will insert a bare (control) left arm into the cage for 1 minute to assess biting activity of the midges. Only cages with at least 10 midges landing within one minute will be used in the tests. This same procedure is used to assess whether volunteers are attractive to the midges. The number of midges probing or biting the arm after 1 minute will be counted and recorded (to provide biting rate data of the control test for the Protective Efficacy endpoint) and the arm removed from the cage.

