9.2. Data analysis

The endpoint for Complete Protection Time will be time to treatment failure for each participant test. Treatment failure is the time at which the product no longer provides complete protection, which is determined as the time at which one probe or bite occurs in a 1 minute test, followed by a confirmatory probe or bite within 30 minutes. Using IBM SPSS Statistics 20, the times to treatment failure will be analysed using Kaplan-Meier Survival functions, and from these the median Complete Protection time and 95% confidence intervals will be calculated.

A linear regression will be used to compare the mean complete-protection time for the tested repellents. As a sensitivity analysis we will use linear regression to estimate the mean CPT difference between groups, but we will generate robust standard errors by relaxing the assumption of independence of observations between the same participant within the study, allowing for correlation between observations from the same participant in the variance-covariance matrix.

The Protective Efficacy over time from application will be calculated using the formula below at each hour and presented as a summary table and graph. Using IBM SPSS Statistics 20, the PE will be analysed using a two-way analysis of variance followed by Tukey's tests or generalised linear model.

$$PE = \frac{\text{Midges probing on control} - \text{Midges probing on treatment}}{\text{Midges probing on control}} \times 100$$

Adverse Events will be tabulated and included in the study report. Adverse events occurring after the end of participant participation but before the end of the study will be listed separately.

10. Safety and Data Monitoring

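### Product order is left unspecified, and randomisation is ruled out for a reason that does not bear on order, so product can be confounded with visit or midge cohort in the CPT comparison

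*Combined protocol and SAP*

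**What the plan says.** Section 3 describes a single-arm study in which every participant tests both PMD formulations and the Picaridin control, and adds: "There is no blinding or randomisation employed, since the outcome measures are based on midge behaviour". Section 5 has randomisation in its heading, but it begins "Volunteers will be recruited through standard recruitment methods, including emails, posters, leaflets" and goes on only to participant information and consent. Sections 6 and 8 do not say which product is tested at which visit.

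The products cannot be tested side by side. Section 8.3 puts the product on the right arm and keeps the left arm as the untreated control, and the synopsis says "The minimum interval between the two repellency tests will be 72 hours". Each test uses its own midges: "One cage of midges is used on one volunteer only and after the test, those midges are destroyed" (Section 3.2.1).

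For the primary comparison, Section 9.2 says "A linear regression will be used to compare the mean complete-protection time for the tested repellents". The sensitivity analysis there changes only the standard errors. The synopsis instead names a two-way analysis of variance with Tukey's tests, or "general linear mode will be used to compare the mean complete-protection time for the tested repellents", without naming the factors.

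Several controls on the midges are stated: "Female midges will be host-seeking, of uniform age and 3-8 days post-emergence" (Section 8) and "Only cages with at least 10 midges landing within one minute will be used in the tests" (Section 8.1). Section 8.3 repeats the untreated-arm check hourly and refreshes a cage that falls short.

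**The concern.** Every between-product comparison in this design is also a between-visit comparison. That midges produce the outcome may bear on blinding. It gives no ground for leaving the sequence of products uncontrolled.

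The stated controls limit drift but do not equalise biting pressure between visits. Ten landings from a cage of 50 is a floor with no ceiling, and midge age may lie anywhere from 3 to 8 days. CPT ends at a confirmed probe or bite, or at more than one in a single test, so it plausibly depends on how hard the cage is biting. The untreated-arm count rescales protective efficacy but does not enter CPT.

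Cage differences that are independent across participants only add noise. A shift shared across participants and aligned with product would bias the CPT comparison, which is part of the primary objective. Each product's Kaplan–Meier median would also carry the conditions of its visit. The robust standard errors planned as a sensitivity analysis cannot remove a bias in the estimate.

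**Working it through.** **1. SD behind the plan's sample size.** Appendix 4 does not state the SD, so I back-solved it from its formula, rounding up:

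n = 2σ²/δ² × (z₁₋α/₂ + z₁₋β)²

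With δ = 120 min, α = 0.05/2 = 0.025, power 80% and σ = 68.9 min: 2 × 68.9²/120² × (2.2414 + 0.8416)² = 6.27, which rounds up to the stated 7. In steps of 0.1 min, the Bonferroni table is matched in all 15 cells for σ from 68.9 to 69.1, and the uncorrected table in all 15 for σ from 68.4 to 68.9. Only 68.9 matches all 30. This recovers the plan's assumption; it does not validate it.

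**2. Can visit be separated from product?** A model with 7 participant, 2 product and 2 visit parameters has 11 columns.

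- One common order for all 7 participants: rank 9 of 11. Product and visit are fully aliased.
- Six orders plus one repeated: rank 11 of 11.

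**3. What a visit shift would do under one common order.** Assumptions: no true product difference; one shift common to all participants between the two visits compared; normal errors with SD 68.9 min and within-participant correlation ρ; product-only regression with 18 residual df; t = difference/√(2s²/7). The SE of a product difference is 68.9 × √(2/7) = 36.8 min, so a 60 min shift is 60/36.8 = 1.63 SEs. False-positive rates from 200,000 simulated trials per setting:

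| Shift (assumed) | Nominal 5%, ρ = 0 | Nominal 5%, ρ = 0.5 | Nominal 2.5%, ρ = 0 | Nominal 2.5%, ρ = 0.5 |
|---|---|---|---|---|
| 0 min | 5.0% | 1.1% | 2.5% | 0.4% |
| 30 min | 12.1% | 6.3% | 7.1% | 3.0% |
| 60 min | 33.9% | 30.2% | 23.5% | 18.6% |

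The zero-shift row shows that at ρ = 0.5 the product-only model is conservative, because it ignores the pairing. The inflation there starts from about 1%, not 5%.

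**4. The same 60 min shift with balanced orders.** With all six orders once and one repeated, each product falls at each visit 2 or 3 times out of 7. A 60 min shift at one visit therefore leaves a bias of at most 60 × (3/7 − 2/7) = 60/7 = 8.6 min. Simulating shift patterns (0, 0, 60), (0, 60, 60) and (0, 60, 0) with the product-only regression, the highest false-positive rate is 3.9% at nominal 5% and 1.8% at nominal 2.5%, even without a visit term.

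**5. Cost of the model terms.** With balanced orders, the variance of a product difference is 0.2917σ² with the visit term and 2/7 = 0.2857σ² without it: 0.2917/0.2857 = 1.02, about 2% more. Residual df fall from 12 to 10. Power at 120 min and α = 0.025:

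| Model | ρ = 0 | ρ = 0.5 |
|---|---|---|
| Product only (18 df) | 78% | 84% |
| Participant + product (12 df) | 75% | 97% |
| Participant + product + visit (10 df) | 72% | 96% |

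**The case against.** Bias needs both a largely common order and a shift shared across participants, and the documents state neither. Order is unspecified, not fixed, and staff might vary it in practice. Midge exposure is set up cage by cage for each volunteer. Standardisation is substantial: reference-strain midges, fixed rearing and room conditions, selected host-seeking females, a landing check before every exposure, pre-test rules for participants, and each participant as their own comparator. All of this is correct. It makes the confounding possible rather than certain and a large shift less likely, but it does not exclude a shift. Cages can share a batch, and the landing check sets only a minimum.

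The 60 min figure is also a choice: 60/68.9 = 0.87 SD, half the 120 min design difference and a whole test interval. A 15 min shift gives only about 2–7% at nominal 5%. The simulation ignores the hourly grid and the 12-hour limit. If times are recorded at the next hourly test and capped at 720 min, a 60 min shift gives 28–32% for an assumed mean CPT of 300 min and 16–20% for 650 min. These points stand: the rates are illustrations and should not be read as expected values.

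Finally, controlling order is enough to remove most of the bias. The participant term addresses within-participant correlation, which the robust standard errors partly cover, and it costs power if that correlation is zero. This is fair. The order change stands without the model terms, although participant and visit terms are standard for a within-participant design. The two-way analysis of variance in the synopsis could include participant, but it does not say so.

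**Conclusion.** The concern holds. The plan rules out randomisation on a ground unrelated to product order, sets no order, requires separate visits and names no visit term for CPT. It therefore permits product and visit to be aliased in the primary comparison, and if a common order is used this cannot be undone afterwards.

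The size is unknown because the documents give no visit or cohort effect. Under the stated assumptions (common order, common shift, SD 68.9 min, correlation 0 to 0.5), inflation at nominal 5% runs from modest at 30 min (about 6–12%) to serious at 60 min (about 30–34%), and less at 60 min if many tests reach the 12-hour limit. This should be fixed before testing begins. The sample size of 7 is not in dispute here.

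**What to change.** - **Sections 3 and 5:** randomise the 7 participants to the six possible product orders, each used once and one used twice. Remove the dependence of the outcome on midge behaviour as a reason for not randomising order.
- **Section 10.3:** add visit number and midge cage or batch to the CRF. Date of visit is already collected, so cage or batch is the information that is missing.
- **Section 9.2 and the synopsis:** specify participant and visit as terms in the CPT comparison model. Once order is balanced, the visit term removes only the small residual imbalance.

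The cost is an allocation list, a small CRF addition and short protocol edits, with no extra participants, visits or staff. Relative to the product-only regression, adding participant and visit moves power at 120 min and α = 0.025 from about 78% to 72% if within-participant correlation is 0, and from about 84% to 96% if it is 0.5. If the sponsor prefers not to accept the lower figure, the order change should still be made on its own.

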3.1. Study Endpoints

The primary endpoint is the median Complete Protection Time (CPT) of the repellent products. The CPT is defined as the time between application of the repellent product and the occurrence of the first probe or bite in a 1 minute test, followed by a confirmatory probe or bite within 30 minutes.

The secondary endpoint is an assessment of the products Protective Efficacy (PE) over time. Protective Efficacy over time will be expressed as the percentage of midges probing or biting at hourly intervals from the time of the repellent application to the end of the test (when 50% or more midges are probing or biting the test arm vs. untreated control, or 12 hours).

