8.2. Product application

The products will be applied to the forearm between the wrist and elbow. Volunteers' forearm surface area is estimated using the WHO protocol for testing skin repellents below:

$$Area = \frac{1}{2} (C_W + C_E) \times D_{EW}$$

Where C_W is the circumference of the wrist; C_E is the circumference of the elbow; and D_{EW} is the distance between the wrist and elbow in centimetres (cm). The dose is expressed using $\mu\text{l}/\text{cm}^2$. The appropriate dose is then measured using a micropipette or balance and applied to the arm using a gloved finger.

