8.3. Complete Protection Time

The repellent product will be applied to the right arm of the participant. A combined fitness check and control test is conducted as described in section 8.1. Immediately after, the right (treated) arm is inserted into the cage for 1 minute. The number of midges probing or biting the arm after 1 minute will be counted and recorded. A further hour post-application of the repellent product, the left arm (control) of the volunteer is again inserted into the cage. The number of midges probing or biting the arm after 1 minute will be counted and recorded and the arm removed from the cage. If less than 10 midges land on the untreated arm during this 1 minute test the cage will be refreshed with new midges and the test repeated. Immediately after, the right (treated) arm is again inserted into the cage for 1 minute. The number of midges probing or biting the arm after 1 minute will be counted and recorded. This procedure will be repeated at hourly intervals throughout the test.

If at any stage, more than one midge probes or bites on the treated arm in the 1 minute test, this represents the end of the testing for Complete Protection Time. If, at any stage, one midge probes or bites on the treated arm in the 1 minute test the test will be repeated half an hour later. If there is a confirmatory probe or bite during the test, this represents the end of the testing for Complete Protection Time but testing for Protective Efficacy (as described in section 8.4) will continue at hourly intervals, with the next test taking place 30 minutes later. If there is no confirmatory probe or bite during this test, testing will resume, with the next test to take place 30 minutes later. All testing for Complete Protection Time and Protective Efficacy must be conducted at hourly intervals.

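### Blinding is waived because outcomes rest on midge behaviour, but a person judges each probe and a count of 0, 1 or more sets the CPT, so the primary endpoint is open to observer bias

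*Combined protocol and SAP*

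**What the plan says.** Section 3 gives a single reason for an open design: "There is no blinding or randomisation employed, since the outcome measures are based on midge behaviour". Section 3.1 times failure from application to "the occurrence of the first probe or bite in a 1 minute test, followed by a confirmatory probe or bite within 30 minutes", and section 9.2 repeats this definition.

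Section 8.3 describes how the outcome is obtained. At each exposure, "The number of midges probing or biting the arm after 1 minute will be counted and recorded". The treated-arm count has three consequences:

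- With no probe, testing goes on to the next hour: "This procedure will be repeated at hourly intervals throughout the test".
- If "one midge probes or bites on the treated arm in the 1 minute test the test will be repeated half an hour later", a second probe at that retest confirms failure.
- If "more than one midge probes or bites on the treated arm in the 1 minute test, this represents the end of the testing" for CPT, no retest is needed.

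Section 8.1 uses landings to judge whether a cage is fit for use, but records probing or biting as the outcome. The protocol thus treats the two as different observations.

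On the products, section 6 says "NEO-INNOVA HEALTHCARE LIMITED will provide two products to be tested containing 35% and 40% PMD, and one positive control", all at one application rate. Section 8.2 says "The appropriate dose is then measured using a micropipette or balance and applied to the arm using a gloved finger". Section 10.3 places product details in the same visit record as the probe counts. The protocol describes no coded product, masked counter, second reader or video record, and it does not define a probe.

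**The concern.** The rationale treats the behaviour and the record of it as the same thing. Knowing the product cannot alter what a midge does. It can alter how a doubtful contact is read during a one-minute exposure in a cage of fifty small flies. Masking protects that reading, and the endpoint turns on very small counts.

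The objectives are comparative: two sponsor formulations against a marketed product, with results intended for label claims. A misreading that is the same for all products would shift every CPT but largely cancel in the comparison. A misreading that depends on knowing the product would not cancel. With 7 participants, a few calls carry weight.

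**Working it through.** **1. The design figure.** Appendix 4 uses n = 2σ²(z₁₋α/₂ + z₁₋β)²/δ², with δ = 120 min, power 80% and α = 0.05/2 = 0.025. It gives no σ. Solving backwards, σ of about 69 min reproduces all 15 Bonferroni cells, so I assume 69:

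n = 2 × 69² × (2.241 + 0.842)² / 120² = 6.29, rounded up to 7. The plan's figure is reproduced.

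**2. What one miscall does to a session's CPT.** Under sections 3.1 and 9.2, failure is timed at the first probe that is later confirmed. First probes arise at hourly tests, and the half-hour retest only confirms. I assume that a count of more than one is timed at the test where it is seen.

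| Miscall | Change in recorded CPT |
|---|---|
| Spurious single probe, not confirmed | 0 |
| Two probes read as one, then confirmed | 0 |
| One probe read as two, where the retest would have confirmed | 0 |
| First probe missed | later by at least 60 min |
| Confirmatory probe missed | later by at least 60 min |
| One probe read as two, where the retest would not have confirmed | earlier by at least 60 min |
| Spurious single probe, followed by a real probe at the retest | earlier by at least 60 min |

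A probe missed at the last, 12-hour test instead leaves the session with no recorded failure. Otherwise the smallest non-zero change is 60 min, and 60/120 is half of the design difference.

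**3. Illustration for a product mean.** Assume one 60-minute step in the same direction in 3 of 7 sessions: 3 × 60/7 = 25.7, or about 26 min. The documents give no miscall rate, so the 3 is arbitrary. The range is 60/7 = 8.6 min for one session to 60 min for all seven.

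**4. What such a shift would do to a comparison.** This uses the same independent-groups normal approximation as Appendix 4, with σ = 69 and n = 7. The standard error is 69 × √(2/7) = 36.9 min and the critical value is 2.241. For a shift b that affects one product only:

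- False-positive rate = 1 − Φ(2.241 − b/36.9) + Φ(−2.241 − b/36.9).
- Power against a true 120 min when the shift works against it ≈ Φ((120 − b)/36.9 − 2.241).

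| Shift b (min) | False-positive rate per comparison | Power |
|---|---|---|
| 0 | 2.5% | 84% |
| 8.6 | 2.9% | 78% |
| 25.7 | 6.3% | 62% |
| 60 | 27% | 27% |

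These rows show sensitivity only. They do not estimate the bias in this trial.

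**The case against.** Several points on the other side are fair.

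- **The counter is not named.** This stands. That the counter knows the product is an inference from the stated absence of blinding and from product details sitting beside the counts in section 10.3.
- **The confirmatory rule and the untreated arm give protection.** In part. Confirmation removes isolated false probes. It is read by the same open process, a count above one bypasses it, and it does nothing about missed probes. The untreated arm checks that midges are biting but does not conceal the product.
- **Coding may do least where it matters most.** Appendix 4 powers only PMD against Picaridin, and odour or appearance may give that contrast away. The documents describe neither, so how well masking would work is unknown. This limits the remedy but does not rescue the rationale.
- **Handling differs.** Section 3.2.2 cites a PMD-specific handling procedure, and section 8.2 allows either a micropipette or a balance. Using the same precautions and the same measuring method for all three products deals with both.

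A reader might infer that the counts will favour the sponsor's products. The documents do not support that. Testing is done at a subsidiary of an academic institution, not by the sponsor, and nothing shows that bias occurs or which way it would run. A reader might also infer that every miscall shifts the CPT. The first table shows that several do not.

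**Conclusion.** The point holds as a vulnerability in the design, not as evidence of bias. The section 3 reason for an open design does not hold, because the endpoint is a human reading of midge behaviour and depends on one or two probes. On the section 3.1 definition, a miscall costs a session nothing or at least 60 minutes, half of the design difference. The 26-minute shift in a product mean rests on an assumed three one-directional miscalls in seven sessions. The false-positive and power figures rest in addition on a back-solved SD of 69 min and on the independent-groups approximation. The true size and direction cannot be known from the documents. The change should be made because partial masking is cheap and the rationale needs correcting in any case.

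**What to change.** Have the three products supplied or decanted into identical coded containers. Measure and apply them in the same way, with the same handling precautions for all. Record only the code in the case report form's product field. Let the sponsor, or an existing team member who does not count bites, hold the key. It should be available for safety at any time and otherwise broken after database lock.

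Replace the rationale in section 3. State as a limitation that odour or appearance may make masking partial, especially for PMD against Picaridin. A written definition of a probe, as distinct from a landing, would complement the coding.

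The cost is minor preparation work and a code list. No extra assessor, participant or visit is needed. The downside is that masking may be incomplete.
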